9.10 Dose Interruptions and Modifications

Although entinostat and atezolizumab have distinct toxicity profiles, they do share some AEs such as fatigue and nausea. There is also the possibility that 1 agent may potentiate the other and hence drug causality will not always be clear. In the event of uncertainty, dose reductions or delays will follow the most conservative approach (i.e., delays and/or dose reductions for both drugs) until resolution of the event, or the patient is taken off study. However, if the toxicity is clearly associated with only one of the study drugs, then the other study drug may be continued at the discretion of the study investigator in consultation with the Medical Monitor, until resolution of the event or the patient is taken off study.

Note: If a patient permanently discontinues either study drug (entinostat/placebo or atezolizumab), the patient will be taken off study treatment

No dose reductions will be performed for atezolizumab.

Guidance for entinostat delays and or dose reductions can be found in Protocol [Section 9.10.1](#) . All dose modifications should be based on the AE requiring the greatest modification and should be properly documented in source documents. Investigators may take a more conservative approach than the guidelines outlined in the protocol on the basis of clinical judgment that is in the best interest of the subject. Such instances should be reported to the Medical Monitor.

Expected AEs for each agent are summarized in [Section 12](#).

9.10.1 Entinostat

In Phase 1b, dose delays, but not dose reductions will be allowed for entinostat during Cycle 1.

If a dose reduction is required during Cycle 1, the patient will be taken off study. Dose delays for reasons other than toxicities definitely or possibly related to entinostat should be avoided as much as possible during Cycle 1.

In Phase 2, both dose delays and dose reductions will be allowed as described below. Once the entinostat dose is reduced, it cannot be re-escalated.

9.10.1.1 Non-hematologic Toxicity at Least Possibly Related to Entinostat

The rules outlined in [Table 9-1](#) are to be followed for the management of non-hematologic toxicities that are definitely or possibly due to entinostat alone, with toxicities graded by the Investigator according to the NCI, CTCAE, version 4.03. Note: No dose reduction is allowed during the first study treatment cycle in phase 1b.

Table 9-1 Non-hematologic Toxicity: Dose Modifications for Entinostat

Toxicity	Dose modifications
Grade 4	
Administer symptomatic remedies/ start prophylaxis.
 
Hold¹ dose until recovery to Grade 1 or baseline under the following directions.
 
1. If recovered within 4 weeks of onset (ie: ≤3 missed doses) , resume study drug as follows:
• If receiving 5 mg, restart study drug at 3 mg• If receiving 3 mg, restart study drug at 2 mg• If receiving 2 mg, discontinue study treatment2. If dose is held for 4 consecutive weeks, permanently discontinue study drug.
Grade 3	
Administer symptomatic remedies/ start prophylaxis.
 
Hold¹ dose until recovery to Grade 1 or baseline under the following directions:
 
1. If recovered by next scheduled dose, resume study drug at prior dose. If not recovered by next scheduled dose, continue to hold the dose.2. If recovered within 2-4 weeks (i.e. missed 3 or less doses) resume study drug as follows:
• If receiving 5 mg, restart study drug at 3 mg.• If receiving 3 mg, restart study drug at 2 mg.• If receiving 2 mg, discontinue study treatment. 
If dose is held for 4 consecutive weeks, permanently discontinue study drug.

Recurrence of the same Grade 3 toxicity despite dose reduction	
Administer symptomatic remedies / start prophylaxis.
 
If receiving 2 mg, permanently discontinue study drug. Otherwise, hold¹ dose until recovery to Grade 1 or baseline.
 
1. If recovered within the next 2 scheduled doses, resume study drug as follows:
• If receiving 5 mg, restart study drug at 3 mg• If receiving 3 mg, restart study drug at 2 mg2. If the same ≥Grade 3 event recurs (i.e., 3 occurrence) despite entinostat dose reduction to 2 mg, as described above, discontinue study drug.
≤Grade 2	
Administer symptomatic remedies / start prophylaxis.
 
Dosing of study drug may be interrupted at the Investigator's discretion, in consultation with the Medical Monitor.
 
• If dose is held for 4 consecutive weeks, permanently discontinue study drug.¹• If toxicity resolves, resume entinostat at the original dose.

¹ If greater than 50% of doses are missed during any 6 week period, discontinue from study drug treatment.

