9.10.1.2 Hematologic Toxicity at Least Possibly Related to Entinostat

The guidelines in [Table 9-2](#) will be followed for determining the timing of cycles based on hematologic status at the time of planned dosing. Note: No dose reduction is allowed during the first study treatment cycle during phase 1b.

Table 9-2 Hematologic Toxicity: Dose Modification for Entinostat

Toxicity	Dose modifications
≥Grade 3 neutropenia, ≥Grade 3 uncomplicated thrombocytopenia, or Grade 2 complicated thrombocytopenia	Administer symptomatic remedies/ start prophylaxis. Hold dose ¹ until recovery to Grade 1 or study baseline using the following directions: 
1. If recovered by next scheduled dose, resume study drug at prior dose. If not recovered by next scheduled dose, hold the dose.2. If recovered within the next 2-4 weeks (i.e. missed 3 or less doses) resume study drug as follows:
• If receiving 5 mg, restart study drug at 3 mg.• If receiving 3 mg, restart study drug at 2 mg.• If receiving 2 mg, permanently discontinue study drug.3. If not recovered within 4 weeks (i.e. 4 doses missed), permanently discontinue study drug.
Recurrence of the same hematologic toxicity	Administer symptomatic remedies/ start prophylaxis. If receiving 2 mg, permanently discontinue study drug. Otherwise, hold ¹ dose until recovery to Grade 1 or baseline. 
1. If recovered within the next 2 scheduled doses, resume study drug as follows:
• If receiving 5 mg, restart study drug at 3 mg• If receiving 3 mg, restart study drug at 2 mg2. If the same ≥Grade 3 event recurs (i.e., third occurrence) despite entinostat dose reduction to 2 mg, as described above, discontinue study drug.

¹ If greater than 50% of doses are missed during any 6 week period, discontinue from study drug treatment.

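### Table 9-1's recurrence row does not fit its own heading, so a promptly resolving Grade 3 recurrence at an unreduced 5 mg dose can be restarted at 5 mg or at 3 mg

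*Protocol*

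**What the plan says.** Protocol 9.10.1.1 says that the rules in Table 9-1 "are to be followed for the management of non-hematologic toxicities that are definitely or possibly due to entinostat alone". Two of its rows matter here.

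- **Grade 3 row.** Item 1: "If recovered by next scheduled dose, resume study drug at prior dose". Item 2 steps the dose down one level after a longer hold with no more than three missed doses. The row is not limited to a first occurrence.
- **Recurrence row.** The heading is "Recurrence of the same Grade 3 toxicity despite dose reduction". The opening line is "If receiving 2 mg, permanently discontinue study drug. Otherwise, hold". Item 1 covers recovery within two scheduled doses and begins "If receiving 5 mg, restart study drug at 3 mg", followed by a step from 3 mg to 2 mg. Item 2 stops the drug if the "event recurs (i.e., 3 occurrence) despite entinostat dose reduction to 2 mg, as described above, discontinue study drug".

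Section 9.10.1 adds: "Once the entinostat dose is reduced, it cannot be re-escalated". The dose levels are 5, 3 and 2 mg weekly, starting at 5 mg (Synopsis, 6.1, 6.3).

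Table 9-2 (9.10.1.2), for hematologic toxicity, has a recurrence row with the same opening line and the same step-down bullets. Its heading is only "Recurrence of the same hematologic toxicity" and carries no condition about an earlier reduction.

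**The concern.** The heading limits the row to patients who have already been reduced, but the first bullet addresses patients at the top dose. Either the heading is too narrow or the bullet is left over.

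The gap is a practical one, because the Grade 3 row lets a patient reach a second identical event without any reduction. For that patient, two sites could apply the same table and give different doses. What is at stake is re-exposure at full dose after a Grade 3 toxicity that has already come back, and consistent handling across up to about 50 centers.

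**Working it through.** The plan states no figure to reproduce. The check traces the dosing rules.

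**Step 1: can a reduced patient be on 5 mg?** The ladder is 5, 3, 2 mg, so a reduction from the top leaves 3 or 2 mg. Re-escalation is barred. That sentence stands in the Phase 2 paragraph of 9.10.1, but no route back to 5 mg is described for Phase 1b either. The row for Grade 2 or lower speaks of resuming at the original dose, which is most naturally the dose before that hold. So under its own heading, the 5 mg bullet fits nobody.

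**Step 2: can an unreduced patient have a recurrence?** Yes. A first Grade 3 event at 5 mg that clears in time for the next weekly dose returns her to 5 mg under item 1 of the Grade 3 row.

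**Step 3: what happens at the second identical event on 5 mg?**

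| Recovery | By the heading (Grade 3 row) | By the bullet (recurrence row) |
|---|---|---|
| In time for the next dose | 5 mg | 3 mg |
| One dose missed | 3 mg | 3 mg |

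The recurrence row's window of two scheduled doses includes recovery by the very next one, so the overlap is real.

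**Step 4: size of the difference.** There are three doses per 21-day cycle (days 1, 8, 15). For prompt recovery from the second event:

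- RP2D 5 mg: 3 × 5 = 15 mg versus 3 × 3 = 9 mg; (15 − 9)/15 = 40% lower.
- RP2D 3 mg: 3 × 3 = 9 mg versus 3 × 2 = 6 mg; (9 − 6)/9 = 33% lower.
- RP2D 2 mg: 3 × 2 = 6 mg versus discontinuation. Under 9.10, stopping entinostat permanently also ends atezolizumab on study.

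These are steps of the dose ladder, not estimates of harm.

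**Step 5: does another clause decide between the rows?** Section 9.10 has three candidates, and none does.

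- The conservative-approach rule applies when it is unclear which drug caused the event.
- The greatest-modification rule chooses between adverse events, not between two rows for one event.
- The investigator's freedom to be more cautious is optional.

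**Step 6: does item 2 show the intent?** Its count of three fits a sequence in which every event brings a reduction (5 to 3, 3 to 2, stop), which favors the heading. But Table 9-2 carries the same item 2 under a heading with no such condition. The count does not settle the question.

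**The case against.** The best reply is that a row heading defines who the row covers. An unreduced patient is outside it, the Grade 3 row gives her one answer, and the 5 mg bullet is merely inert. Different rules for hematologic and non-hematologic toxicity would be an ordinary choice. This reading is legitimate and may be the intended one, which is why the intent needs confirming. It does not remove the defect, because a mandatory table still contains an instruction that contradicts its heading and that a site could reasonably follow.

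It also stands that the 5 mg reading is not unguarded. Symptomatic treatment or prophylaxis, and recovery to Grade 1 or baseline, come before any re-dose. Investigators may step down on their own judgement, and unacceptable toxicity ends treatment.

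A reader might infer more than the documents support:

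- **That the rows agree whenever a dose is missed.** They agree at one missed dose. At three, the Grade 3 row still gives 3 mg, while the recurrence row gives no restart dose. That shorter window is shared with Table 9-2 and is a separate choice.
- **That at most 10% × 35 = 3.5 patients are affected.** Section 12.1.1 reports that neutropenia was the only Grade 3 or 4 event above 10% in an earlier breast cancer study. That limit applies to each event type, whereas affected patients accumulate across types. The base of 35 also omits Phase 1b patients, who follow Table 9-1 after Cycle 1.
- **That the gap widens greatly with further recurrences.** This needs three or four identical, promptly resolving Grade 3 events with no investigator acting.
- **That Table 9-2 is also defective.** Its opening line already stops the drug on any recurrence at 2 mg.

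**Conclusion.** The inconsistency is real on the text, but minor. It concerns an unreduced patient with the same Grade 3 non-hematologic event, attributed to entinostat alone, occurring twice and clearing in time for the next weekly dose each time. For her, the table supports two restart doses one level apart: 15 versus 9 mg per cycle at an RP2D of 5 mg. Read by the heading, it never requires a step-down for such recurrences.

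The conclusion rests on 5 mg being the highest dose in use and on the absence of any route back to it after a reduction. The number affected cannot be derived from the documents and is probably small. The intended rule is not certain; Table 9-2 suggests, without proving, that the qualifier in the Table 9-1 heading is the error. There is no effect on sample size, power or alpha.

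**What to change.** Delete the last three words of the recurrence-row heading in Table 9-1. Any recurrence of the same Grade 3 toxicity then steps down one level (5 to 3 mg, 3 to 2 mg, discontinue at 2 mg), as in Table 9-2. The medical monitor should confirm that this is intended. If the intent is to resume the same dose after a promptly resolving recurrence, keep the heading and delete the 5 mg bullet instead.

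Removing the occurrence count from item 2 of Table 9-1 is optional tidying. After the heading is corrected, the patient traced above has her events at 5, 5, 3 and 2 mg, so the one at 2 mg is her fourth. No outcome changes, because the row's opening line already stops the drug at 2 mg. Table 9-2 needs no change.

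The cost is a short text edit in the next amendment. A few patients with promptly resolving recurrences would be reduced sooner or, if the RP2D is 2 mg, would come off both drugs after a second event.

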9.10.1.2 Hematologic Toxicity at Least Possibly Related to Entinostat

The guidelines in [Table 9-2](#) will be followed for determining the timing of cycles based on hematologic status at the time of planned dosing. Note: No dose reduction is allowed during the first study treatment cycle during phase 1b.

Table 9-2 Hematologic Toxicity: Dose Modification for Entinostat

Toxicity	Dose modifications
≥Grade 3 neutropenia, ≥Grade 3 uncomplicated thrombocytopenia, or Grade 2 complicated thrombocytopenia	Administer symptomatic remedies/ start prophylaxis. Hold dose ¹ until recovery to Grade 1 or study baseline using the following directions: 
1. If recovered by next scheduled dose, resume study drug at prior dose. If not recovered by next scheduled dose, hold the dose.2. If recovered within the next 2-4 weeks (i.e. missed 3 or less doses) resume study drug as follows:
• If receiving 5 mg, restart study drug at 3 mg.• If receiving 3 mg, restart study drug at 2 mg.• If receiving 2 mg, permanently discontinue study drug.3. If not recovered within 4 weeks (i.e. 4 doses missed), permanently discontinue study drug.
Recurrence of the same hematologic toxicity	Administer symptomatic remedies/ start prophylaxis. If receiving 2 mg, permanently discontinue study drug. Otherwise, hold ¹ dose until recovery to Grade 1 or baseline. 
1. If recovered within the next 2 scheduled doses, resume study drug as follows:
• If receiving 5 mg, restart study drug at 3 mg• If receiving 3 mg, restart study drug at 2 mg2. If the same ≥Grade 3 event recurs (i.e., third occurrence) despite entinostat dose reduction to 2 mg, as described above, discontinue study drug.

¹ If greater than 50% of doses are missed during any 6 week period, discontinue from study drug treatment.

9.10.2 Atezolizumab

There will be no dose reduction for atezolizumab in this study.

Patients may temporarily suspend study treatment for up to 84 days beyond the last dose if they experience adverse events that require atezolizumab to be withheld. If atezolizumab is withheld because of atezolizumab related adverse events for >84 days beyond the last dose, then the patient will be discontinued from study treatment and will be followed up for safety and efficacy per protocol.

If, in the judgment of the investigator, the patient is likely to derive clinical benefit from atezolizumab after a hold of >84 days, and entinostat has been administered per protocol during this time, study drug may be restarted only with the approval of the Medical Monitor.

As discussed in Protocol [Section 9.12](#), systemic corticosteroids should be used to treat immune mediated toxicities related to atezolizumab. If a patient must be tapered off steroids used to treat adverse events, atezolizumab may be held for additional time beyond 84 days from the last dose until steroids are discontinued or reduced to prednisone dose (or dose equivalent) \leq 10 mg/day. The acceptable length of interruption will depend on an agreement between the investigator and the Medical Monitor.

Dose interruptions for reason(s) other than toxicity, such as surgical procedures, may be allowed with Medical Monitor approval. The acceptable length of interruption will depend on agreement between the investigator and the Medical Monitor .

9.11 Concomitant Therapy

All concomitant treatments and therapies, or medication, including all prescription, over-the-counter, herbal supplements, and IV medications and fluids, administered during the 30 days preceding the screening study visit must be reported in the electronic case report form (eCRF). If changes occur during the study period, documentation of drug dosage, frequency, route, and date should also be included on the eCRF. The generic name of the drug (or trade name for combination drugs) must be specified along with the route of administration, indication, and duration of treatment.

Throughout the study, the Investigator may prescribe any concomitant medications or treatments deemed necessary to provide adequate supportive care, such as potassium and phosphorus supplements and antiemetics, with the exception of those listed in [Section 9.12](#).

No premedication will be allowed for the first dose of atezolizumab. Premedication may be administered for subsequent infusions at the discretion of the treating physician after consultation with the Medical Monitor. Patients must notify the Investigator of all concomitant medications taken through completion of the study (30 day follow-up safety visit).

Medications or vaccinations specifically prohibited in the exclusion criteria are not allowed during the ongoing study ([Section 9.12](#)). If there is a clinical indication for any medication or vaccination specifically prohibited during the study, discontinuation from study drug will be required. The Investigator should discuss any questions regarding this with the Medical Monitor.

The final decision on any supportive therapy or vaccination rests with the Investigator and/or the patient's primary physician. However, the decision to continue the patient on study drug requires the mutual agreement of the investigator, the Medical Monitor and the patient.

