6. Received a live vaccine within 30 days of the first dose of treatment (inactivated forms of influenza vaccinations can be given during influenza season only (approximately October to March in the Northern hemisphere and April to September in the Southern Hemisphere).
7. Prior anti-cancer monoclonal antibody (mAb) within 4 weeks prior to study enrollment or who has not recovered (i.e., ≤Grade 1 at enrollment) from AEs due to mAb agents administered more than 4 weeks earlier.

8. Prior chemotherapy within 3 weeks, targeted small molecule therapy or radiation therapy within 2 weeks prior to study enrollment or who has not recovered (i.e., \leq Grade 1 at enrollment) from AEs due to a previously administered agent.

Note: Patients with \leq Grade 2 neuropathy or \leq Grade 2 alopecia are an exception to this criterion and may qualify for the study.

9. Received transfusion of blood products (including platelets or red blood cells) or administration of colony stimulating factors (including granulocyte-colony stimulating factor [G-CSF], granulocyte macrophage-colony stimulating factor [GM-CSF], or recombinant erythropoietin) within 4 weeks prior to the first dose of treatment.
10. Currently participating and receiving study therapy or has participated in a study of an investigational agent and received study therapy or used an investigational device within 4 weeks of the first dose of study drug.
11. Currently receiving treatment with any other agent listed on the prohibited medication list (protocol [section 9.12](#))
12. If female, is pregnant, breastfeeding, or expecting to conceive starting with the screening visit through 120 days after the last dose of study drug.
13. Known history of human immunodeficiency virus (HIV) (HIV 1/2 antibodies).
14. Known active hepatitis B (e.g., hepatitis B surface antigen-reactive) or hepatitis C (e.g., hepatitis C virus ribonucleic acid [qualitative]). Patients with past hepatitis B virus (HBV) infection or resolved HBV infection (defined as the presence of hepatitis B core antibody [HBc Ab] and absence of HBsAg) are eligible. HBV DNA test must be performed in these patients prior to randomization. Patients positive for hepatitis C virus (HCV) antibody are eligible only if polymerase chain reaction is negative for HCV RNA.
15. Allergy to benzamide or inactive components of entinostat.
16. History of allergies to any active or inactive ingredients of atezolizumab.

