9.12 Prohibited Medication

The following medications are excluded while the patient is receiving study treatment:

- Any other HDAC inhibitor, including valproic acid
- DNA methyltransferase inhibitors
- Any additional investigational or commercial anticancer agents, such as chemotherapy, immunotherapy, targeted therapy, biological response modifiers, or endocrine therapy, will not be allowed, even if utilized as treatment of non-cancer indications.
- Prophylactic use of hematopoietic colony stimulating factors are not allowed during the Phase 1b, but can be used per investigator discretion during other parts of the study.
- Radiation therapy

Note: Radiation therapy to a symptomatic solitary lesion or to the brain may be considered on an exceptional case-by-case basis after consultation with the Medical Monitor. The radiation field cannot encompass a target lesion. Radiation to a target lesion is considered progressive disease and the subject should be removed from study treatment. The patient must have clear measurable disease outside the radiated field. Administration of palliative radiation therapy will be considered clinical progression.

- Traditional herbal medicines; these therapies are not fully studied and their use may result in unanticipated drug-drug interactions that may cause or confound the assessment of toxicity
- RANKL inhibitor (denosumab): patients who are receiving denosumab prior to randomization must be willing and eligible to receive a bisphosphonate instead while on study
- Immunomodulatory agents, including but not limited to interferons or IL-2, during the entire study; these agents could potentially increase the risk for autoimmune conditions when received in combination with atezolizumab
- Immunosuppressive medications, including but not limited to cyclophosphamide, azathioprine, methotrexate, and thalidomide; these agents could potentially alter the activity and the safety of atezolizumab
- Use of steroids to premedicate patients for whom CT scans with contrast are contraindicated (i.e., patients with contrast allergy or impaired renal clearance); in such patients, MRIs of the chest, abdomen, and pelvis with a non-contrast CT scan of the chest must be performed
- Any live, attenuated vaccine (e.g., FluMist®) while the patient is receiving atezolizumab and for a period of 90 days after the discontinuation of atezolizumab

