12. ADVERSE EVENTS, DATA REPORTING, AND RECORDING

12.1 Study Drugs

12.1.1 Entinostat

Commonly encountered AEs across clinical studies of entinostat monotherapy in patients with solid tumors included hypoalbuminemia, fatigue, nausea, hypophosphatemia, anemia, and thrombocytopenia. Incidence and severity were dose- and schedule-dependent. In a Phase 2, randomized, placebo-controlled study in patients with breast cancer, in which patients received exemestane+entinostat or exemestane+placebo, treatment-emergent adverse events (TEAEs) occurring at a $\geq 10\%$ higher incidence in entinostat-treated patients versus placebo-treated patients included fatigue (48% vs 26%), nausea (40% vs 15%), neutropenia (30% vs 0%), peripheral edema and vomiting (both 21% vs 5%), thrombocytopenia (19% vs 6%), pain (16% vs 6%), and dyspepsia and leukopenia (both 14% vs 3%). The only Grade 3 or 4 AE occurring at a $>10\%$ incidence for entinostat vs placebo was neutropenia (14% vs 0%). In a Phase 2 study in patients with metastatic melanoma treated with entinostat monotherapy, the most common TEAEs were nausea (39%), hypophosphatemia (29%), pain in extremity (21%), and back pain and diarrhea (each 18%) ([Hauschild 2008](#)).

Additional clinical experience is summarized in the entinostat IB. As stated previously, there are no clinical data with entinostat in combination with atezolizumab.

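### Protocol 9.11 and the end of 9.12 turn pre-entry medication exclusions into grounds for stopping study drug, in conflict with on-study permissions in 9.12, 9.10.2 and 9.14

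*Protocol*

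**What the plan says.** **Strict text.** Protocol 9.11 states "Medications or vaccinations specifically prohibited in the exclusion criteria are not allowed during the ongoing study", with a pointer to 9.12. The next sentence reads "If there is a clinical indication for any medication or vaccination specifically prohibited during the study, discontinuation from study drug will be required". Section 9.12 closes by saying that further prohibited medications are to be found in the exclusion criteria (7.2). Under 9.9 and 9.10, permanently stopping either entinostat/placebo or atezolizumab takes the patient off all study treatment.

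**What the exclusion criteria name.** Criterion 9 in 7.2 covers "Received transfusion of blood products (including platelets or red blood cells) or administration of colony stimulating factors", within 4 weeks before first dose. It lists G-CSF, GM-CSF and recombinant erythropoietin as examples. Criterion 1 covers systemic steroids and other immunosuppressive therapy within 7 days before first dose.

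**Permissive text.** Section 9.12 bars prophylactic colony stimulating factors in Phase 1b, "but can be used per investigator discretion during other parts of the study". Section 9.10.2 says that "systemic corticosteroids should be used to treat immune mediated toxicities related to atezolizumab" and provides for holding and resuming atezolizumab. Many of the 9.14 tables direct steroids and then allow atezolizumab to resume. Section 9.12 also allows dose- or duration-limited systemic steroids for other acute conditions.

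**The concern.** An eligibility window keeps certain treatments out of the run-up to first dose. It does not say what should happen when a patient on study needs the same treatment. Section 9.11 draws no such line, so its literal wording makes a transfusion, a colony stimulating factor or a steroid course a reason to end study drug, although other sections permit or direct some of these.

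Up to about 50 international centers may take part. A patient with Grade 3 neutropenia given G-CSF, or one given a transfusion, could continue at one site and lose both drugs at another. If the need for the treatment differs by arm, the rule would also remove background atezolizumab unequally and mix a procedural stop into the PFS comparison.

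**Working it through.** **1. The design figure.** Inputs from Protocol 13.1.2 and 13.2: 60 PFS events, medians 4 vs 7 months (HR 4/7 = 0.571), one-sided alpha 0.1, one O'Brien-Fleming interim at 45 events.

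- Expected Z at 60 events: |ln(4/7)| × √60 / 2 = 0.5596 × 3.873 = 2.167.
- Power without an interim: Φ(2.167 − 1.282) = 0.812.
- With Lan-DeMets O'Brien-Fleming-type boundaries (1.576 at 45 events, 1.380 at 60), power at 60 events is 0.801.

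The plan's 80% is reproduced and is not in dispute.

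**2. The passages side by side.**

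| Class | Named at entry | Strict reading (9.11, end of 9.12) | Text pointing the other way |
|---|---|---|---|
| Colony stimulating factors | Criterion 9, 4 weeks before first dose | Stop study drug | 9.12: prophylactic use at discretion outside Phase 1b; therapeutic use not addressed |
| Transfusion, erythropoietin | Criterion 9, same window | Stop study drug | General wording only: the 9.11 supportive-care sentence excepts just the 9.12 list, and 9.12 allows other medications judged medically necessary |
| Systemic steroids | Criterion 1, 7 days before first dose | Stop study drug | 9.10.2 and 9.14 direct them, with atezolizumab resumable; 9.12 allows limited courses |

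Criterion 9 lists erythropoietin as an example of a colony stimulating factor, while 9.12 does not name it. Whether the 9.12 permission reaches it is therefore also unclear.

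**3. Does the softening text decide the matter?**

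- The 9.12 exception for cases noted otherwise attaches to the treatments listed before it. The sentence bringing in the exclusion criteria comes afterwards and has no exception.
- Section 9.11 points to 9.12, and 9.12 points back to 7.2, so the cross-reference is circular.
- Section 9.11 says "the decision to continue the patient on study drug requires the mutual agreement of the investigator, the Medical Monitor and the patient". This stands beside a flat requirement to discontinue, and neither sentence is made subject to the other.

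**4. Size, for colony stimulating factors only.** Protocol 12.1.1 reports Grade 3 or 4 neutropenia of 14% vs 0% in the earlier randomized exemestane combination study. Assume that those rates carry over and that every such case receives a colony stimulating factor: 35 × 0.14 = 4.9 entinostat patients, against 35 × 0 = 0 on placebo.

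**5. Illustrative effect on power.** Assume that a share q of the entinostat arm stops at once and loses all benefit, so that HR = exp[(1 − q) × ln(4/7)], with the boundaries of step 1.

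| q | Entinostat patients of 35 | HR | Power at 60 events |
|---|---|---|---|
| 0 | 0 | 0.571 | 0.80 |
| 5% | 1.75 | 0.588 | 0.77 |
| 14% | 4.9 | 0.618 | 0.71 |

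If those patients instead revert to the control hazard at month 1, simulation (60 events, unstratified log-rank, no interim adjustment) gives an HR of about 0.60 and power of about 0.73 at 14%. The gap between 0.71 and 0.73 comes largely from the assumption about when benefit is lost.

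**6. How the primary analysis would be affected.** Under Protocol 13.5.5, disease assessments continue after treatment stops, and under 13.3 patients are analysed as randomized. Stopping alone does not censor primary PFS. Any effect comes through lost exposure, censoring at new anticancer therapy (13.5.5; SAP 6.1, Table 1) and SAP sensitivity analysis 3, which censors non-progression discontinuations.

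**The case against.** The best defence is that the protocol can be read permissively. The 9.11 sentence points to 9.12, criteria 1 and 9 are pre-dose windows that need not count as on-study prohibitions, specific permissions can prevail over a general sentence, and 9.11 refers questions to the Medical Monitor. All of this stands, and it makes the problem an ambiguity with a literal conflict rather than an unqualified rule. It does not remove the conflict, because nothing says which sentence governs.

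Stronger readings are tempting but unsupported:

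- **That the rule falls mainly on the entinostat arm for all three classes.** Directed steroid use is for atezolizumab toxicity, both arms receive atezolizumab, and no rates by arm are given. For transfusion, anemia is not among the events that 12.1.1 lists as at least 10% more frequent on entinostat. Thrombocytopenia is listed (19% vs 6%), but with no transfusion rate no imbalance in transfusion can be derived.
- **That the any-grade neutropenia rate (30% vs 0%, so 35 × 0.30 = 10.5 patients) sets the size.** Table 9-2 acts on neutropenia only from Grade 3, and the documents give no rate of colony stimulating factor use.
- **That Table 9-2 itself directs colony stimulating factors.** Its instruction, "Administer symptomatic remedies/ start prophylaxis", names none, and Table 9-1 uses the same phrase for non-hematologic toxicity.
- **That power is lost by a known amount.** The figures are upper-bound illustrations for a class whose prophylactic use 9.12 expressly permits in Phase 2.

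**Conclusion.** The point holds as a conflict in the current text. Read literally, 9.11 and the last sentence of 9.12 require study drug to stop for treatments that 9.12, 9.10.2 and 9.14 permit or direct, and they leave transfusion and erythropoietin unresolved. Because stopping one drug ends both, the reading a site adopts changes what its patients receive.

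An effect that differs by arm is plausible for colony stimulating factors only. It reaches at most about 5 of 35 entinostat patients against 0, and rests on three assumptions: rates from an exemestane combination carry over, every Grade 3-4 neutropenia is treated with one, and sites apply the strict reading. If only 5% of the arm were affected, power would fall from about 80% to 77% even with immediate loss of all benefit. No imbalance is shown for steroids or transfusion, and the documents do not support a firm figure for lost power.

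**What to change.** Reconcile 9.11 and the last sentence of 9.12 with the rest of 9.12, 9.10.2 and 9.14. State once, separately for colony stimulating factors (prophylactic and therapeutic), transfusions and erythropoietin, and systemic corticosteroids, whether on-study use ends study treatment. Which rule applies is for the sponsor to decide; the need is that the sections agree.

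In the SAP, add a table by arm of the use of these classes and of related treatment discontinuations. The planned outputs tabulate concomitant medications by generic name, and adverse events leading to discontinuation by system organ class and preferred term. Neither groups these classes or links their use to stopping. Section 9.11 already asks sites to record all concomitant treatments and therapies.

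The cost is protocol wording and one table, with no new patients or assessments.
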